12.2 Definition of Estimands in the CASH Trial

We define two primary estimands corresponding to the intention-to-treat (ITT) and per-protocol (PP) analyses, as well as an additional estimand incorporating neurological mortality.

12.2.1 Primary Estimand – Intention-to-Treat (ITT) Analysis

This estimand aims to assess the effect of cilostazol added to nimodipine on the modified Rankin Scale (mRS) at 6 months, considering all randomized patients, regardless of intercurrent events.

- Target Population: All randomized patients.
- Variable of Interest: mRS at 6 months, dichotomized as favorable outcome (mRS 0-2) vs. unfavorable outcome (mRS 3-6).
- Handling of Intercurrent Events:
 - Early treatment discontinuation → "Treatment Policy" strategy: Patients remain in their randomized group, regardless of treatment adherence.
 - Death before 6 months → "Composite" strategy:
 - Neurological death → Counted as mRS=6.
 - Non-neurological death → Counted as mRS in ITT analysis and a secondary analysis excluding these patients.
 - Loss to follow-up → "Composite" strategy: Last observation carried forward (LOCF) with multiple imputation as a sensitivity analysis.
- Estimation Method: Logistic regression adjusted for age and initial severity (GCS grade) and centre.

◆ Justification: This approach respects the ITT principle, ensures comparability between groups, and provides a realistic assessment of treatment effect.

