5.3 End of research visit at 6 months

The end of research visit will be made at 6 months or when the patient terminates the study.

Primary outcome

The physician, physical therapist, research assistant or research nurse will collect blindly the mRS if the patient is alive. A face-to-face structured interview will be held during which the modified Rankin scale will be assessed (Appendix 1, 17).

Functional and cognitive status will be collected during the patient's consultation at 6 months, with using:

- SAHOT Score
- MOCA score
- Return to work
- Activities of Daily Living
- Instrumental Activities of Daily Living

The in-hospital morbidity indicators will be collected, including:

- Length of Intensive Care Unit stay
- Length of hospital stay

The occurrence of cerebral vasospasm and DCI during ICU stay will be assessed, with collecting

-Delayed cerebral ischemia, defined as the occurrence of focal neurological deficit or a decrease of at least 2 points on the Glasgow Coma Scale, which does not occur immediately after aneurysm occlusion and which is not ascribable to other causes.

[figure not shown]
-Cerebral artery vasospasm, defined as a reduction of the diameter of the proximal cerebral artery on either CT-, MR- or catheter angiography

-Cerebral infarcts, considered when detected on the CT scan or MRI performed with 6 weeks, (or on the latest CT scan or MRI performed before death within 6 weeks, or at autopsy), but not present on the earlier CT or MRI scan performed between 24 and 48 h after early aneurysm occlusion and not ascribable to other causes

5.4 Expected length of participation and description of the chronology and duration of the research.

Inclusion period	42 months
The included subjects' length of participation, of which:	

 • Treatment period: • Follow-up period: 	2 weeks 6 months
Total research period:	49 months

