The time-to-event variables will be analysed using the Cox proportional hazards model, including randomisation arm, age (as a continuous variable), severity at inclusion, and centre as model terms. The hazard ratio between the arms will be presented with the 95% CI and p-value of the model. Kaplan-Meier curves will be presented by the arm for each appropriate endpoint.

For the primary objective, both overall and by subgroups, the following statistics will be provided: effect size, confidence intervals, number needed to treat and absolute risk reduction as appropriate.

All tests will be two-sided with a unilateral significance level of 0.025% adjusted for the interim analysis.

Subgroup analyses

Subgroup analyses will be performed to assess the consistency of the treatment effect between subgroups without multiplicity adjustment. The following subgroups will be assessed for the primary endpoint:

- Fisher grade I to III versus IV
- Age: <50 years; >=50 and <=70 years; >70 years

The treatment effect for the total population and subgroups will be represented using forest plot graphs.

For HR and OR in subgroup analyses, the significance of the interaction will be tested using the method proposed by Altman & Bland 2003.

Treatment of missing data

For the analysis of the primary endpoint, in the event of study exit prior to evaluation of the primary endpoint (6 months), the last recorded mRS value will be used (LOCF method, mRS at ICU discharge) patients will be considered as non responders if no mRS are recorded.

For all other variables, in case of a significant proportion of missing data (>10% of subjects), a sensitivity analysis using multiple conditional imputation techniques by chained equations (MICE) will be performed, according to a conservative principle, using the mean severity at inclusion as the central position parameter and an estimate of the intra-patient variability in the placebo group as the dispersion parameter. Sensitivity analysis based on imputed data will be considered secondary.

Further details on the treatment of missing data will be provided in the SAP.

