12.2.3 Additional Estimand – Impact of Mortality on the Analysis

An additional estimand will be conducted to specifically evaluate the impact of neurological vs. non-neurological mortality:

- Target Population: All randomized patients.
- Variable of Interest: mRS at 6 months, considering:
 - mRS=6 for neurological deaths.
 - Exclusion of non-neurological deaths in a secondary analysis.

◆ Justification: This analysis differentiates the specific effects of treatment on neurological mortality, which is crucial for interpreting the trial results.

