Stage	Information proportion	Beta spent this stage	Cumulative beta spent	Percentage beta spent at this stage	Cumulative percentage
1	0.33	0.0264	0.0264	13.2	13.2
2	0.67	0.0901	0.1165	45.7	58.3
3	1.00	0.0835	0.2000	41.7	100.0

Boundary Probabilities for $\delta = -0.11$

Number of Simulations: 100000

Futility Boundaries: Binding

After Efficacy Boundary Crossing: Hold Out

After Binding Futility Boundary Crossing: Hold Out

 Alternative Hypothesis: $P1 - P2 < 0$ (one-sided)

P1: 0.65

P2: 0.76

 δ : -0.11

Stage	N1	N2	Efficacy		Futility	
			Boundary	Probability	Boundary	Probability
1	95	95	-3.7103	0.0253	0.2701	0.0277
2	189	189	-2.5111	0.4166	-1.1224	0.0885
3	284	284	-1.9308	0.3597	-1.9308	0.0821

Average N1: 226.

Average N2: 226

[figure not shown]

Figure 1.

12.6 Specify if subjects who leave the research prematurely will be replaced and in what proportion.

The primary outcome is assessed only one time 6 months after Day 0 (5 months and a half after last day of treatment) that could lead to patient's loss to follow up. Nevertheless, SAH is a serious condition that requires a long and close patient's monitoring. That will limit patient's loss to follow up. The patients who leave study prematurely (for loss to follow up or death) won't be replaced and will be considered as non responder patients in the main analysis of primary criterion.

Some sensitivity analyses will be performed with complete cases only.

Only, the particular circumstance of patient resignation will lead to exit patient of the primary analysis. A 10% rate of non evaluable patients is foreseen.

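### Sections 12.1, 12.2.1/12.3 and 12.6 of the protocol give different rules for scoring deaths in the primary analysis, and non-neurological death has no stated value

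*Protocol*

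**What the plan says.** Four places in the protocol bear on how a death enters the primary analysis.

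- **Section 12.2.1 (primary ITT estimand).** All deaths before six months are placed under a composite strategy and then split by cause. For the first group the rule is "Neurological death → Counted as mRS=6". For non-neurological death it is "Counted as mRS in ITT analysis and a secondary analysis excluding these patients", with no grade. LOCF stands in a separate bullet, for loss to follow-up.
- **Section 12.3 (table of intercurrent events).** Neurological death again has the value 6. The row for non-neurological death names the composite strategy and a sensitivity analysis, but no value. Section 12.2.3 has the same split: "mRS=6 for neurological deaths", and an exclusion of the other deaths in a secondary analysis.
- **Section 12.1 (treatment of missing data).** The rule is that "in the event of study exit prior to evaluation of the primary endpoint (6 months), the last recorded mRS value will be used". The value meant is the mRS at ICU discharge, and non-response is assigned only when no mRS is on record. Death is not mentioned.
- **Section 12.6.** Patients who leave early, with loss to follow-up and death both named as reasons, "will be considered as non responder patients in the main analysis of primary criterion". Cause of death plays no part.

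Section 5.3 adds that the assessor at six months "will collect blindly the mRS if the patient is alive". The structured interview in Appendix 1 lists grades 5 down to 0. The value 6 for a death therefore has to come from a scoring rule and not from the interview.

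**The concern.** Death is the worst category of the primary endpoint, so its score should not depend on which section the analyst opens first. The estimand sections give 6 to one class of death and nothing to the other, and the same split recurs across 12.2.1, 12.2.3 and 12.3. A single slip of the pen is thus a less comfortable explanation than it would be if the omission occurred once.

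The gap matters because a second rule could fill it. Section 12.1 applies to study exits, and 12.6 itself lists death among the ways of leaving the study early. Section 5.2 has an mRS recorded at ICU discharge, so a patient who dies later has a value available to carry forward. If that value is 0-2, a literal application of 12.1 gives a favourable outcome to a patient who has died.

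The same three sections also disagree on loss to follow-up: LOCF in 12.1 and 12.2.1, non-response in 12.6. That contradiction is plainer than the one on deaths, and it weakens 12.6 as a tie-breaker. An analyst who uses LOCF for loss to follow-up has already departed from the sentence in 12.6 that also covers deaths.

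**Working it through.** **1. The rules side by side.** Each row is a patient without a six-month mRS interview.

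| Patient | 12.1 read literally | 12.2.1 and 12.3 | 12.6 |
|---|---|---|---|
| Neurological death after ICU discharge at mRS 0-2 | responder (carried forward) | mRS 6, non-responder | non-responder |
| Non-neurological death after ICU discharge at mRS 0-2 | responder (carried forward) | composite, no value | non-responder |
| Death with no mRS on record | non-responder | mRS 6 if neurological, otherwise no value | non-responder |
| Lost to follow-up, ICU-discharge mRS 0-2 | responder (carried forward) | responder (LOCF) | non-responder |

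For neurological deaths the explicit value 6 answers 12.1. For deaths with no recorded mRS, 12.1 and 12.6 agree. What is left open is non-neurological death after ICU discharge in a patient discharged at mRS 0-2 (row 2). Row 4 is a direct contradiction.

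**2. The planned design, reproduced.** Inputs from section 12.5: 65% against 76%, one-sided alpha 0.025, power 0.80, looks at 95, 189 and 284 per arm, efficacy boundaries -3.7103, -2.5111 and -1.9308, and binding futility boundaries 0.2701, -1.1224 and -1.9308. A simulation of 1,000,000 trials with an unadjusted pooled z statistic gives power 0.800 (plan: 0.8016) and one-sided error 0.0251 (plan: 0.025). The second futility boundary is the one printed in 12.5; section 12.7 prints -1.224.

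**3. Size if 12.1 were applied literally.** The protocol gives no rate of non-neurological death after ICU discharge, so every rate here is an assumption.

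Assume 1% to 3% of 630 patients die this way and half of them left the ICU at mRS 0-2:

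- 630 × 0.01 × 0.5 = 3.15 patients; 630 × 0.03 × 0.5 = 9.45 patients.
- All in one arm of 315: 3.15 / 315 = 1.0 point; 9.45 / 315 = 3.0 points.
- Planned difference: 76 - 65 = 11 points.

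A wider grid takes such deaths as 1%, 2% or 5% of one arm, with 25% to 100% of them discharged at mRS 0-2. The number mis-scored in that arm runs from 315 × 0.01 × 0.25 = 0.8 to 315 × 0.05 × 1 = 15.8. With true response 65% in both arms, and these deaths in the cilostazol arm only, the simulated one-sided rejection rate is:

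| Deaths, share of cilostazol arm | Rejection rate (25% to 100% discharged at mRS 0-2) |
|---|---|
| none | 0.025 |
| 1% | 0.029 to 0.043 |
| 2% | 0.033 to 0.071 |
| 5% | 0.049 to 0.24 |

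If such deaths are equally frequent in both arms, the 11-point difference is unchanged and simulated power lies between 0.802 and 0.845 over the same grid. If 12.6 is followed, none of these patients is mis-scored.

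**4. Ceiling for loss to follow-up.** The drop-out allowance is 10%, and 630 × 0.10 = 63 patients. That is the most who could be scored differently under LOCF and under 12.6. It would be reached only if the whole allowance were loss to follow-up with an ICU-discharge mRS of 0-2.

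**The case against.** A reader might infer that the plan will count dead patients as responders. The documents do not support that.

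- Section 12.2.1 gives death its own heading, under a composite strategy for both causes, and attaches LOCF to a different event.
- The conversion table in 12.5 lists grade 6 as dead, without regard to cause, and 4.1.1 puts grades 3-6 in the unfavourable class. On this scale a death is an observed outcome, while the LOCF sentence stands under missing data.
- Section 5.2 says the ICU-discharge mRS is taken in case of loss to follow-up, which shows its purpose.
- Section 12.6 states the non-response rule for deaths outright.
- The simplest reading of the unfinished phrase in 12.2.1 is a dropped value of 6.

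The size can also be challenged. Section 5.8.1.1 stops study treatment when the patient leaves the ICU, and 2.6 gives a half-life of about 11 hours. A large drug-related excess of deaths confined to the period after discharge is not something the protocol suggests.

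Most of this stands, and it removes the strong reading. It does not remove the disagreement. The composite label settles less than it seems to, because 12.2.1 and 12.3 put the same label on loss to follow-up handled by LOCF. Section 12.6 cannot decide the matter alone while its rule on loss to follow-up contradicts 12.1 and 12.2.1. And 12.1, as written, does not except deaths.

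**Conclusion.** The protocol's rules for scoring deaths in the primary analysis conflict, and the primary estimand gives no value for non-neurological death. The intended answer is very probably non-response for every death, but the text should say so.

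The effect on the result is zero under 12.6. Under the literal reading of 12.1 it is small when such deaths are balanced between arms. The shift of 1 to 3 points needs three things together: the assumed 1-3% rate, half of those patients discharged at mRS 0-2, and all of them in one arm. It is an extreme case and not an expected bias. The rejection rates above rest on the same one-sided allocation and on an unadjusted test at 284 per arm, not on the planned adjusted logistic regression.

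The contradiction on loss to follow-up does not depend on any reading: LOCF and non-response cannot both be the primary rule.

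**What to change.** - In 12.2.1 and in the table of 12.3, replace the split by cause with one line for the primary analysis: death from any cause before six months is scored mRS 6 (non-responder) in the primary ITT analysis.
- Keep the exclusion of non-neurological deaths as a secondary analysis only.
- In 12.1, state that LOCF never applies to a patient known to have died.
- Reconcile 12.1 and 12.2.1 with 12.6 on loss to follow-up: name either LOCF or non-response as the primary rule, and move the other to the sensitivity analyses.

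The cost is a few lines in a protocol amendment, best made before the first interim analysis so that all looks use the same scoring. No new data are needed, and the primary score no longer depends on how a death is classified by cause. The 284 per arm and 630 in total stay as they are, because the 65% and 76% refer to mRS 0-2 with death already inside 3-6.

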4.2.4 Randomisation

After screening for inclusion and non-inclusion criteria, and obtaining consent, patients will be randomized (1:1 ratio) to cilostazol or placebo groups by logging onto a randomization website using a pre-prepared randomization list, balanced by randomly variable block size. Randomization will be stratified by centre, age (<50 years; >=50 and <=75 Years; >75 years); and severity (Fisher grade from I to III; Fisher grade IV)

"CASH" protocol, version 2.1 of 04/04/2025

Randomisation will occur in an online data entry platform, guaranteeing the concealment of the experimental arm assigned to the doctor performing the inclusion and randomisation of the patient.

The randomisation code will be disclosed once recruitment is completed.

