- Therapy intensity level (Annexe 5)

Clinical examination at the time of inclusion:

- SAH severity according to WFNS,
- GCS score,
- Neurological focal sign at admission
- Anisocoria

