All categorical variables will be summarised by treatment with numbers and percentages of participants.

All continuous variables, including changes from baseline, will be summarised by treatment with means, standard deviations or medians and interquartile range [IQR] for skewed variables.

The following formula will be used, depending on how the post-basal endpoint is defined, for each scheduled visit and for each time point at which both baseline and post-basal values are available:

- Change from baseline = post-baseline value - baseline value
- Percentage change from baseline = $(\text{post-baseline value} - \text{baseline value})/\text{baseline value} \times 100\%$
- Ratio to baseline = post-baseline value / baseline value

Primary objective

The analysis of clinical effectiveness will be performed on the ITT population.

For the assessment of the primary objective, the percentage of patients who responded to treatment per experimental arm will be evaluated. Specifically, treatment will be considered effective when mRS at six months is ≤ 2 .

Therefore, the treatment response variable will be dichotomised as follows

0 if the mRS is > 2 (non-responder patient)

1 if the the mRS value is ≤ 2 (responders).

A logistic regression model adjusted by centre, age (continuous), and severity at inclusion, considering the dichotomised value of the mRS (≤ 2 , > 2) as the response variable, and will be used. Consequently, the efficacy of the experimental treatment will be expressed as an adjusted Odds Ratio, and the 95% confidence interval and NNT index will be provided.

Sensibility analysis

The described analysis for the assessment of clinical efficacy will be repeated in the per-protocol population and after the replacement of missing data of mRS at six months, on the one hand, according to a "worst case scenario" logic and on the other hand, using multiple imputations.

Secondary efficacy analyses

Secondary analyses of clinical effectiveness will be performed on the ITT population. Analyses on per protocol population may be carried out.

A logistic regression model adjusted by centre, age (continuous) and severity at inclusion will be used considering the dichotomised mRS value at six months (≤ 1 versus > 1).

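### Randomisation stratifies severity by Fisher grade, but the primary model in 12.2.1 adjusts for an undefined GCS grade and leaves the Fisher stratum out, while 12.1 names no severity scale

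*Protocol*

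**What the plan says.** All references are to the protocol.

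- **4.2.4 Randomisation.** The strata are centre, three age bands and "severity (Fisher grade from I to III; Fisher grade IV".
- **12.1, primary objective.** "A logistic regression model adjusted by centre, age (continuous), and severity at inclusion". No scale is given for severity.
- **12.1, secondary efficacy.** The mRS 0-1 model repeats the term: "A logistic regression model adjusted by centre, age (continuous) and severity at inclusion will be used". The Cox models use "age (as a continuous variable), severity at inclusion, and centre as model terms".
- **12.1, subgroups.** Fisher appears by name, as "Fisher grade I to III versus IV".
- **12.1, missing data.** The imputation of other variables is described as "using the mean severity at inclusion as the central position parameter".
- **12.2.1, primary estimand.** "Logistic regression adjusted for age and initial severity (GCS grade) and centre".
- **5.1 Inclusion visit.** WFNS and GCS are recorded as severity at hospital admission, and Fisher is listed with the first CT findings. Under "Clinical examination at the time of inclusion" the word severity is attached to WFNS, and the GCS score is a separate item.

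**The concern.** A primary analysis should be specified so that two statisticians working from the same protocol fit the same model, and that model would normally carry the factors used to stratify randomisation. Here centre and age carry through from randomisation to analysis, but severity changes scale. The section that defines the primary estimand uses a different measure from the one used to randomise, and the section that describes the primary analysis leaves the measure open.

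What is at stake is a little efficiency and the uniqueness of the primary model. The same open term also enters the mRS 0-1 model, the Cox models and the imputation text.

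**Working it through.** **1. The text side by side**

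| Place | Severity term |
|---|---|
| 4.2.4, randomisation | Fisher I-III / IV |
| 12.1, primary, mRS 0-1 and Cox models | severity at inclusion, scale not named |
| 12.1, subgroups | Fisher I-III / IV |
| 12.2.1, primary estimand | GCS grade |
| 5.1, examination at inclusion | WFNS called severity; GCS score listed separately |

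The 12.1 term has three possible readings:

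- *Fisher*, because centre, age and severity mirror the strata. Then 12.1 and 12.2.1 specify different primary models.
- *GCS*, because 12.2.1 says so. Then the sections agree, and both omit the Fisher stratum.
- *WFNS*, because 5.1 uses the word severity for it at inclusion. Then the sections differ, and neither includes Fisher.

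Under every reading 12.2.1 lacks the Fisher stratum. No section equates GCS grade with Fisher or says that the stratification factors enter in addition.

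GCS grade is not defined either. Section 5.1 collects GCS as a score, twice, and no grouping is given. The word initial in 12.2.1 suggests admission; the baseline definition in 12.1 (last evaluation before study treatment) suggests inclusion. In the imputation text, a mean of severity has no clear meaning if severity is a two-level Fisher factor.

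**2. The design figures involve no covariates**

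Inputs from 12.5: 0.65 versus 0.76, 284 per arm, one-sided alpha 0.025, three looks.

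Maximum information for an unadjusted difference in proportions = n / [p1(1 − p1) + p2(1 − p2)] = 284 / (0.65 × 0.35 + 0.76 × 0.24) = 284 / 0.4099 = 692.85. The protocol prints 692.8519.

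A simulation of 400,000 trials used z = (p1 − p2) / √[2p̄(1 − p̄)/n], looks at 95, 189 and 284 per arm, and the boundaries tabulated in 12.5. It gave power 0.800 (protocol 0.8016) and type I error 0.0252 (protocol 0.025). The choice of severity covariate therefore cannot change the planned sample size.

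**3. Power lost by omitting Fisher**

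The protocol gives no prevalence or prognostic effect for Fisher or GCS, so these are assumptions:

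- Fisher IV in 55% of patients; Fisher odds ratio 1, 0.5 or 0.33.
- Three GCS levels with odds ratios 1/0.8/0.6 (weak), 1/0.5/0.2 (medium) or 1/0.4/0.1 (strong).
- GCS independent of Fisher (levels 50/25/25%), or correlated with it (65/22/13% in Fisher I-III, 35/28/37% in Fisher IV).

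The simulation used 568 patients, blocks of 4 or 6 within 9 centres × 3 age bands × 2 Fisher strata, and marginal rates of 65% and 76%, with 2,500 trials per cell. The logistic models contained treatment, centre, age and the severity terms shown. For this exercise only, the Wald z was compared with the 12.5 boundaries. The unadjusted test in the same trials averaged 0.808.

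Three-look power, GCS only → GCS plus Fisher:

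| Setting | Weak GCS | Medium GCS | Strong GCS |
|---|---|---|---|
| Independent, Fisher OR 1 | 0.811 → 0.813 | 0.843 → 0.845 | 0.880 → 0.880 |
| Independent, OR 0.5 | 0.828 → 0.836 | 0.840 → 0.847 | 0.870 → 0.873 |
| Independent, OR 0.33 | 0.832 → 0.851 | 0.850 → 0.862 | 0.866 → 0.871 |
| Correlated, OR 0.5 | 0.815 → 0.818 | 0.870 → 0.870 | 0.884 → 0.886 |
| Correlated, OR 0.33 | 0.818 → 0.836 | 0.873 → 0.879 | 0.894 → 0.902 |

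The gain from adding Fisher is −0.04 to 1.88 points (paired standard error up to about 0.3).

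A second, single-look simulation replaced Fisher with a proxy agreeing with it 65% of the time and having no effect of its own. Half the patients were Fisher IV. The loss was 0.831 − 0.828 = 0.003 at a Fisher odds ratio of 1.5, rising to 0.853 − 0.826 = 0.027 at an odds ratio of 5, a more extreme case.

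**4. Type I error**

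Over 15,000 three-look null trials, the one-sided rate was 0.0241 with GCS only, 0.0266 with both and 0.0263 with Fisher only (standard error 0.0013). All lie within about 1.2 standard errors of 0.025, so neither inflation nor an advantage for any model is shown.

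**The case against.** The best defence is that specific text completes general text. Section 12.2.1 names GCS, so 12.1 can be read the same way, leaving one model: centre, age and GCS. The imputation wording, which takes a mean of severity, fits that better than a two-level Fisher factor. Nothing in the protocol promises that the model will mirror the strata, and age is already modelled as continuous although it is stratified in bands. This has force: a flat contradiction between 12.1 and 12.2.1 follows only if 12.1 means Fisher or WFNS. It does not restore Fisher, and it leaves GCS grade without a time point or a form. The age comparison is also imperfect, since continuous age largely carries the information in the bands, whereas GCS is a different measurement from Fisher.

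A second defence is that GCS may be the better covariate. In the simulation, GCS-only power equalled or exceeded Fisher-only power in 11 of 15 cells (Fisher only ranged from 0.806 to 0.860, GCS only from 0.811 to 0.894). That depends on the assumed GCS effects, but it is a reason to add Fisher rather than substitute it for GCS.

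A third is that the SAP may settle the matter. It may, but the protocol is not silent here: it names a scale in 12.2.1 that is not the randomisation factor, and a SAP that adopts Fisher would depart from that text.

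A reader might also infer that the open covariate affects the interim stopping decisions. The documents do not support this. The boundaries in 12.5 are for a difference in proportions, and nothing says that the adjusted logistic statistic is compared with them. Nor can one say how often the choice of scale would change the trial's conclusion: that depends mainly on how prognostic GCS is, which the protocol does not state.

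**Conclusion.** The point holds in a limited form. As written, the primary model in 12.2.1 omits the Fisher stratum used at randomisation. The severity term is not uniquely specified: three candidate scales in 12.1, and an undefined grade in 12.2.1. The cost is about 0 to 2 points of power when Fisher is left out of a model containing GCS, and it rests wholly on assumed prevalences and effects. Type I error is not inflated, and the planned sample size is unaffected. This is worth correcting because the correction is free, not because the trial's validity is in doubt.

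**What to change.** State one covariate set in both 12.1 and 12.2.1: centre, continuous age and the Fisher stratum as randomised (I-III versus IV). If GCS is kept as an additional covariate, say whether it is the admission or the inclusion value, and whether it enters as a score or in defined categories. Use the same set in the mRS 0-1 and Cox models. In the missing-data text, say which variable the mean severity refers to.

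The cost is wording only. Relative to 12.2.1 it adds one binary covariate, already known for every patient at randomisation; GCS is already collected at both times. No new data, patients or procedures are needed.
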